#### **4.4 SAMPLE**

The sample selection consisted on patients referred to the Federal University of Rio Grande do Sul's Dentistry School. The selected patients require bilateral extraction of lower third molars under local anesthesia in two different surgical times. There will be no change to the routine care for patients volunteering in the study. The surgical procedures will be performed by the research team responsible for this study. Participants of both sexes, aged 18 to 50 years, were included in the study if they presented an indication for bilateral surgical removal of mandibular third molars in similar positions according to Pell and Gregory classification. Additional inclusion criteria comprised the absence of systemic comorbidities, local conditions free of inflammatory or infectious processes, no history of allergy to the prescribed medications, and no recent or chronic use of antibiotics, anti-inflammatory drugs, corticosteroids, or analgesics. Participants were excluded from the study if they used medications other than those prescribed by the surgeon, failed to provide the required data, belonged to Group A (control) but used postoperative ice packs, or belonged to Group B (test) and did not use ice packs as instructed by the researchers. There were three dropouts due to noncompliance with postoperative recommendations and the use of non-prescribed medication, resulting in 34 procedures performed in 17 patients.

Postoperative consultations were conducted for follow-up, suture removal, and the evaluation and treatment of any potential postoperative complications.

The selection of the control group and experimental groups were determined by a simple randomization in the immediate postoperative period. One surgical site didn't receive cryotherapy (GA), while the other site received cryotherapy with ice (GB).

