## 4.7 STUDY VARIABLES

The outcome variables of this study were postoperative pain, trismus, local edema, and changes in quality of life following mandibular third molar extraction. Postoperative assessments were performed by the research team, consisting of two calibrated surgeons and one supervising professor, on postoperative days 0 (day of surgery), 2, and 7. The following evaluation protocols were applied:

a) Pain assessment: postoperative pain was assessed using a visual analog scale (VAS– APPENDIX C) ranging from 0 to 10, in which 0 represented no pain, 1–3 mild pain, 3.1–6 moderate pain, and 6.1–10 severe pain. Patients completed the scale at home daily until postoperative day 7.

b) Trismus assessment: trismus was evaluated by measuring maximum mouth opening with the patient seated and the tragus–ala plane parallel to the ground. Patients were instructed to open their mouths three consecutive times, and the mean value was recorded. Measurements were obtained as the interincisal distance in millimeters using a measuring tape. In the absence of maxillary or mandibular incisors, the occlusal edges were used as reference points. Measurements were recorded on postoperative days 0, 2, and 7.

c) Edema assessment: facial edema was measured using the method described by Gabka and Matsumura. Three linear facial measurements were obtained in millimeters with a measuring tape: tragus to pogonion, tragus to oral commissure, and lateral canthus to mandibular angle. The mean of these three measurements was calculated to quantify edema. This assessment was performed preoperatively and on postoperative days 2 and 7.

d) Quality of life assessment: quality of life was evaluated using a questionnaire adapted from the OHIP-14 (APPENDIX D), consisting of 14 dichotomous (yes/no) questions addressing daily functional limitations. The questionnaire included items related to chewing and swallowing ability, dietary changes, alterations in taste, mouth opening, voice changes, speech intelligibility, facial appearance, sleep disturbances, and ability to perform work-related activities. The questionnaire was provided to participants on the day of surgery and completed on postoperative days 0, 2, and 7. At the conclusion of the evaluation period following the second intervention, participants also answered the question: “Which intervention did you perceive as resulting in greater postoperative improvement?”

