#### 4.8 STATISTICAL ANALYSIS

Data normality was assessed using the Kolmogorov–Smirnov test. Parametric analyses were applied to compare groups (control side vs. test side) and postoperative time points (from day 0 to day 7). Continuous variables, including pain intensity (VAS scores), maximum mouth opening (mm), and facial edema (mm), were expressed as means  $\pm$  standard deviation (SD).

A two-way repeated-measures analysis of variance (ANOVA), followed by Fisher's least significant difference (LSD) post hoc test, was used to evaluate the main effects of time and treatment, as well as their interaction, for pain intensity, trismus, and edema. Pain reports were also qualitatively analyzed based on the frequency distribution of pain categories (no pain, mild pain, moderate pain, and severe pain) for both groups.

Associations between pain intensity and trismus or edema were assessed using Pearson's correlation coefficient. Trismus and edema were additionally evaluated using the formulas (Baseline – Postoperative) and (Postoperative – Baseline), respectively. Qualitative data related to quality of life were presented as percentages.

All statistical analyses were performed using SPSS software (version 20.0; IBM Corp., Armonk, NY, USA). Statistical significance was set at  $P < 0.05$ .

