### 5 RESULTS

#### 5.1 POSTOPERATIVE PAIN INTENSITY

The analysis demonstrated significant main effects of treatment ( $F_{(1,16)} = 5.063$ ,  $p = 0.039$ ) and time ( $F_{(7,112)} = 6.254$ ,  $p < 0.001$ ) on postoperative pain intensity (Table 1). Overall, pain scores were higher in Group A than in Group B ( $2.0 \pm 1.2$  vs.  $1.3 \pm 1.1$ ;  $F_{(1,16)} = 5.063$ ,  $p = 0.039$ ).

[figure not shown]

[figure not shown]
Table 1: Average pain levels on every post-operative day for each group. (\*) indicates statistical differences between control and test groups.

In Group A, pain intensity was significantly higher on postoperative days 1 ( $3.59 \pm 0.59$ ;  $p = 0.014$ ) and 3 ( $3.24 \pm 0.55$ ;  $p = 0.005$ ) compared with day 0 ( $1.35 \pm 0.54$ ). No significant differences were observed between day 0 and the remaining postoperative time points ( $p > 0.05$ ).

[figure not shown]
On the test side (Group B), no significant differences in pain intensity were observed between day 0 and any postoperative evaluation ( $p > 0.05$ ), suggesting that cryotherapy effectively prevented postoperative pain exacerbation.

A significant interaction between treatment and time was also observed ( $F_{(7,112)} = 2.689$ ,  $p = 0.013$ ). Pain intensity was higher on postoperative day 1 (Group A:  $3.59 \pm 0.59$  vs. Group B:  $2.12 \pm 0.42$ ;  $p = 0.017$ ) and day 3 (Group A:  $3.24 \pm 0.55$  vs. Group B:  $1.29 \pm 0.33$ ;  $p = 0.007$ ) in the control group compared with the cryotherapy group.

Postoperative pain was absent in 29.4% of control cases and 44.1% of cryotherapy cases. Mild pain was reported by 50.0% of participants in Group A and 47.8% in Group B, whereas moderate pain occurred in 16.9% and 7.4% of cases, respectively. Severe pain was reported by 3.7% of control cases and 0.7% of cryotherapy cases (Graphics 1 and 2).

Graphic 1: Prevalence of reports of moderate to severe pain (4-10 in visual analogic scale) in the total number of reports of pain (1-10 in visual analogic scale) in the control group after day 2 (last day of analgesic medication).

12

Graphic 2: Prevalence of reports of moderate to severe pain (4-10 in visual analogic scale) in the total number of reports of pain (1-10 in visual analogic scale) in the test group after day 2 (last day of analgesic medication).

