## 6 DISCUSSION

Cryotherapy was effective in reducing both the intensity and duration of postoperative pain episodes, as well as shortening the period of mouth opening limitation. Additionally, its use in the postoperative period resulted in a reduced need for rescue medication and a greater patient-perceived improvement over time. These findings support the consolidation of a cryotherapy protocol, contributing to a more predictable postoperative course and improving the management of postoperative complications.

As shown in Table 1, differences in mean pain scores during the first 72 postoperative hours (from day 0 to the end of day 2) appear to be related to the lack of consolidation of the inflammatory response under pharmacological analgesia alone. Pain modulation was only stabilized after postoperative day 3 in both groups, as also reported by Sukegawa et al. However, cryotherapy demonstrated a

beneficial synergistic effect when combined with analgesic medication, resulting in lower pain scores during this critical period. In contrast, analgesic therapy alone was insufficient to adequately control pain in the control group, which exhibited two distinct peaks in pain intensity at 24 and 72 hours postoperatively.

The benefit of cryotherapy for the test group was particularly evident between postoperative days 2 (the last day of analgesic medication) and 3 (the first day without medication). During this transition, pain levels increased in the control group and remained consistently higher than those observed in Group B, even during the consolidation phase of the inflammatory response. These findings suggest that the greater differences in pain intensity are directly associated with the absence of cryotherapy in the control group, despite the use of analgesics.

Pain severity distribution over the seven postoperative days further reinforced these findings (Graphics 1 and 2). Proportionally, extractions performed without cryotherapy were associated with a significantly higher likelihood of moderate-to-severe pain. From a clinical perspective, the absence of cryotherapy increased the probability of requiring rescue medication. This observation is particularly relevant for patients with systemic diseases who already require complex pharmacological regimens, increasing the risk of drug interactions, as well as for individuals susceptible to medication dependence, for whom minimizing drug exposure is essential.

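### Pain-category percentages in Section 5.1 are shares of 136 daily reports per side with no stated denominator and an inconsistent unit, and the Discussion calls moderate-to-severe pain significantly more likely without any reported test of the categories

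*Combined protocol and SAP*

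**What the plan says.** Section 4.4 gives the analysed sample: "resulting in 34 procedures performed in 17 patients", so each group has 17 sites. Section 4.7 says of the pain VAS that "Patients completed the scale at home daily until postoperative day 7", and Section 4.8 analyses "postoperative time points (from day 0 to day 7", which is eight reports per side.

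For the pain categories, the only plan in Section 4.8 is descriptive: "Pain reports were also qualitatively analyzed based on the frequency distribution of pain categories". No test is named for them.

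Section 5.1 changes the unit as it goes:

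- No pain: "Postoperative pain was absent in 29.4% of control cases and 44.1% of cryotherapy cases".
- Mild pain: "Mild pain was reported by 50.0% of participants in Group A and 47.8% in Group B".
- Moderate pain: "moderate pain occurred in 16.9% and 7.4% of cases, respectively".
- Severe pain: 3.7% and 0.7%, again of cases.

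No denominator is given, and no p-value or interval accompanies these figures. The Discussion (Section 6), citing Graphics 1 and 2, states that "extractions performed without cryotherapy were associated with a significantly higher likelihood of moderate-to-severe pain".

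**The concern.** There are two separate problems.

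The first is the unit. A reader who sees 'participants' or 'cases' will take the figures as shares of patients or extractions. Severe pain at 3.7% versus 0.7% then looks like a patient risk, when it is a share of patient-days.

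The second is the inference. In a document that sets significance at P < 0.05, 'significantly' reads as the result of a test. None is reported for the categories. Any valid test would have to allow for two features of the data: eight reports from the same patient on the same side, and both sides coming from the same 17 patients. The next sentence of the Discussion goes on to a clinical statement about rescue medication, so the wording carries weight.

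**Working it through.** **1. Recover the denominator.** Inputs are the percentages in Section 5.1: Group A 29.4/50.0/16.9/3.7 and Group B 44.1/47.8/7.4/0.7. Each set sums to 100.0.

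- As patients or extractions (n = 17): 17 × 50.0% = 8.5, 17 × 47.8% = 8.13, 17 × 44.1% = 7.5, 17 × 3.7% = 0.63. Only multiples of 1/17 (5.88%) are possible, so these fail. 29.4% does equal 5/17, but the set as a whole does not fit. Denominators of 20, 34 and 40 also fail.
- As daily reports (n = 17 × 8 = 136): Group A gives 39.98, 68.00, 22.98, 5.03, that is 40/68/23/5. Group B gives 59.98, 65.01, 10.06, 0.95, that is 60/65/10/1. Both sum to 136, and all eight percentages are reproduced to one decimal.
- A search over denominators up to 399 finds only 136 and its double, 272, that fit both groups. 272 would need 16 reports per patient per side, which the schedule does not provide.

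The ANOVA degrees of freedom in Section 5.1 agree: F(7,112) has 7 = 8 − 1 and 112 = 7 × 16, which is 17 patients with eight days each.

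**2. Look for support for 'significantly'.**

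- Section 4.8: descriptive frequencies only.
- Section 5.1: percentages only. The repeated-measures ANOVA is on mean VAS (treatment F(1,16) = 5.063, p = 0.039), not on the likelihood of a category.
- Graphics 1 and 2: captioned as reports after day 2, scored 4–10, as a share of reports scored 1–10. That is a different period and denominator from the day 0–7 percentages. The cut-off also differs in form from Section 4.7, where moderate pain starts at 3.1; the two agree only if scores are whole numbers.

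**3. Size of the contrast.** Moderate-to-severe reports: A 23 + 5 = 28/136 (20.6%); B 10 + 1 = 11/136 (8.1%).

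If all reports were independent: pooled proportion 39/272 = 0.1434; SE = √(0.1434 × 0.8566 × 2/136) = 0.0425; z = 0.125/0.0425 = 2.94; p = 0.003 (Fisher exact 0.005).

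To allow for repetition and pairing, divide z by √[(1 + 7ρ)(1 − r)]. Here ρ is the correlation between days within a patient's side and r is the correlation between a patient's two sides. The documents give neither, so both are assumed.

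A rough guide to r comes from Section 5.1. Assume that the overall 2.0 ± 1.2 and 1.3 ± 1.1 are patient-level SDs. Then t = √5.063 = 2.25, the SD of the difference is 0.7 × √17/2.25 = 1.28, and r = (1.44 + 1.21 − 1.28²)/(2 × 1.2 × 1.1) ≈ 0.38. Rounding of the means (difference 0.8 to 0.6) allows 0.19 to 0.55. Carrying this from mean VAS to the categories is a further assumption.

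| ρ | 1 + 7ρ | p, r = 0 | p, r = 0.19 | p, r = 0.38 |
|---|---|---|---|---|
| 0.1 | 1.7 | 0.024 | 0.012 | 0.004 |
| 0.2 | 2.4 | 0.058 | 0.035 | 0.016 |
| 0.3 | 3.1 | 0.095 | 0.063 | 0.034 |
| 0.5 | 4.5 | 0.17 | 0.12 | 0.078 |

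With r above 0.38, p would fall further.

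**The case against.** The strongest reply is that this is a matter of wording. Only the mild-pain sentence says 'participants'. Section 4.8 and the Graphics captions speak of reports, and the Discussion sentence opens with a word that signals a comparison of proportions. The main pain conclusion rests on an ANOVA with patient-level error, which respects the repeated, paired structure, and neither the Abstract nor the Conclusion repeats the category claim. All of that stands, and it limits the reach of the point. It does not make 50.0% of 17 participants possible, and it does not supply the missing test.

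Three stronger readings are tempting, and the documents do not support them:

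- *That the investigators ran a pooled test treating 136 reports as independent.* No such test is shown; loose wording is as plausible. The p = 0.003 above is this review's arithmetic, not theirs.
- *That a correct analysis would be non-significant.* Allowing for clustering alone pushes p up, but the split-mouth pairing pushes it down. The table has values on both sides of 0.05.
- *That the severe reports come from one or two patients.* The single Group B report is one patient on one day. The five in Group A could be from one patient or several, and no per-patient data are given.

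**Conclusion.** The point holds on both limbs. The percentages are shares of 136 daily reports per side, are given without a denominator, and are named inconsistently; they cannot be shares of 17 participants or 17 extractions. The 136 is inferred rather than stated, but the fit is exact and agrees with the ANOVA degrees of freedom. The statement of significance for moderate-to-severe pain has no reported test behind it, and neither the ANOVA nor the cited Graphics can stand in for one.

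The observed contrast is 28 versus 11 reports. Its significance is undetermined: the illustrative range of about 0.004 to 0.17 rests wholly on assumed correlations and a normal approximation. The statement might survive a proper analysis; the documents do not show that it does.

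**What to change.** 1. In Section 5.1, label every category as n/136 daily reports per side and print the counts.
2. Add, by side, the number of the 17 patients with any moderate-to-severe day and the distribution of such days per patient. State which VAS cut-off is used.
3. Either compare the sides with a paired patient-level test (Wilcoxon signed-rank on days per patient, or exact McNemar on any such day) and report it as an addition to the descriptive plan, or delete 'significantly' from the Discussion. A logistic GEE clustered on patient is possible, but with 17 clusters and 39 events it would need a small-sample variance correction, so the simpler paired tests are preferable.
4. Cite Graphics 1 and 2 only for what their captions cover.

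The cost is relabelling and, at most, one analysis of data already collected. The downside is that the significance statement may weaken or have to go. The mean-VAS result does not change.

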#### **4.6 POSTOPERATIVE CARE**

In the immediate postoperative period following the first surgical procedure, the allocation of postoperative care—with or without cryotherapy—was randomized using a simple draw. Allocation was determined by the selection of a folded paper indicating Group A or Group B and was supervised by a third party to ensure allocation concealment. When the first surgical site of a patient was assigned to Group A (control), the contralateral site in the second surgical procedure was assigned to Group B (test), and vice versa.

Group A (control) did not receive postoperative cryotherapy. Group B (test) was instructed to apply standardized ice packs (11 × 8.5 × 1 cm), provided by the research team, positioned diagonally to cover both the mandibular angle and the cheek on the operated side. Cryotherapy was initiated immediately after surgery under surgeon supervision and continued for the first 12 postoperative hours, consisting of 30-minute applications followed by 30-minute intervals (total of 12 applications). During the intervals, patients were instructed to store the ice packs in a freezer until the next application.

All participants received identical pharmacological postoperative instructions (APPENDIX B) for both interventions, including paracetamol 1 g every 6 hours for 3 days and mouth rinses with 0.12% aqueous chlorhexidine digluconate twice daily for 7 days, starting on the day following surgery. In cases of persistent pain, trismus, or edema that significantly interfered with daily activities despite the use of prescribed analgesics, patients were instructed to use rescue medication consisting of codeine 30 mg every 4 hours as needed.

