When moderate-to-severe pain reports were isolated and compared with the need for rescue medication after suspension of the standard analgesic regimen, 80% of participants in Group A required rescue medication, whereas no participant in Group B required additional analgesia.

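### The conclusion that cryotherapy reduced rescue medication rests on one percentage from a pain-selected subset, with no counts, pairing or test

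*Combined protocol and SAP*

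**What the plan says.** Section 4.6 offers codeine 30 mg as rescue: "In cases of persistent pain, trismus, or edema that significantly interfered with daily activities despite the use of prescribed analgesics". Use is tied neither to a pain score nor to the period after paracetamol ends.

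Section 4.7 defines the endpoints: "The outcome variables of this study were postoperative pain, trismus, local edema, and changes in quality of life". Rescue use is not among them. In Section 4.8 the repeated-measures ANOVA "was used to evaluate the main effects of time and treatment, as well as their interaction, for pain intensity, trismus, and edema". The section adds Pearson correlations, a frequency distribution of pain categories, and percentages for quality of life. It plans nothing for rescue use.

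The result is one sentence at the end of Section 5.1. It restricts attention to moderate-to-severe pain reports, which are "compared with the need for rescue medication after suspension of the standard analgesic regimen, 80% of participants in Group A required rescue medication". For the cryotherapy side the same sentence gives no percentage and says only: "whereas no participant in Group B required additional analgesia". No other rescue figure appears in the text.

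Section 6 says that cryotherapy lowered the need for rescue and that omitting it raised the probability of needing rescue. It applies this to patients on complex drug regimens and to those prone to dependence. Section 7 lists less rescue medication among the effects shown.

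**The concern.** Sections 6 and 7 make a causal statement about rescue use in the trial. The figure behind it describes something narrower: rescue use given that pain was moderate or severe after the analgesic had stopped. Pain is itself affected by treatment (treatment effect p = 0.039 in Section 5.1). The patients who enter the subset on the control side therefore need not be those who enter it on the cryotherapy side. The within-patient comparison that the split-mouth design provides is lost.

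The reader also cannot tell how many patients the 80% represents. The paired evidence over 17 patients could be weak or very strong, and the text does not show which. At stake is one of the effects in the Conclusion, which Section 6 uses as a clinical argument for the protocol.

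**Working it through.** **Inputs.** 17 patients, each with one control and one cryotherapy side (Section 4.4). Rescue 80% vs none (5.1). Pain-category percentages: Group A 29.4, 50.0, 16.9, 3.7; Group B 44.1, 47.8, 7.4, 0.7 (5.1). Daily pain scores on days 0-7, with day 2 the last analgesic day (4.7, 5.1), so days 3-7 give at most 5 reports per patient. Significance level 0.05, taken as two-sided.

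**1. Is 80% a share of all 17?** No: 13/17 = 76.5% and 14/17 = 82.4%. With a denominator of 17 or less, only 4/5, 8/10 and 12/15 round to 80%.

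**2. Is the unit patients or reports?** The sentence selects reports but counts participants. Section 5.1 uses the second word loosely elsewhere: "Mild pain was reported by 50.0% of participants in Group A and 47.8% in Group B". With 17 patients, 50.0% would be 8.5 people, and 47.8% falls between 8/17 = 47.1% and 9/17 = 52.9%. All eight percentages fit 17 x 8 = 136 daily reports:
- Group A: 40 + 68 + 23 + 5 = 136
- Group B: 60 + 65 + 10 + 1 = 136

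Moderate-to-severe reports over days 0-7 are therefore 23 + 5 = 28 in Group A and 10 + 1 = 11 in Group B. The number after day 2 is not in the text, so 28 is an upper limit for Group A.

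**3. Paired result if the unit is patients.** Assume no other users on either side. With b patients using rescue on the control side only and none on the cryotherapy side only, the exact two-sided McNemar p = 2 x (1/2)^b, capped at 1.

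| 80% means | b | Share of 17 | p |
|---|---|---|---|
| 4/5 | 4 | 23.5% | 2/16 = 0.125 |
| 8/10 | 8 | 47.1% | 2/256 = 0.008 |
| 12/15 | 12 | 70.6% | 2/4096 = 0.0005 |

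For p < 0.05, 5 vs 0 is too few (2/32 = 0.0625) and 6 vs 0 is enough (2/64 = 0.031).

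**4. Paired result if the unit is daily reports.** With up to 28 reports, 16/20 and 20/25 also give 80%. The fewest patients is the number of rescue reports divided by 5, rounded up. The most is one report per patient, up to 17.

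| 80% means | Fewest patients (p) | Most patients (p) |
|---|---|---|
| 4/5 | 1 (1.0) | 4 (0.125) |
| 8/10 | 2 (0.5) | 8 (0.008) |
| 12/15 | 3 (0.25) | 12 (0.0005) |
| 16/20 | 4 (0.125) | 16 (0.00003) |
| 20/25 | 4 (0.125) | 17 (0.00002) |

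Group A users could number anywhere from 1 to 17, so significance cannot be determined.

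**5. What the figure leaves out.** Codeine on days 0-2, and codeine taken for trismus, edema or milder pain, is allowed by Section 4.6 and not reported. The Group B statement may cover all 17 patients after the analgesic ended, or only those in the subset.

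**The case against.** The strongest reply is that 80% against none is a large contrast, that the subset is openly described, and that a unit is named. Much of this stands. The subset is labelled, and participants is the plain reading of the counted unit. The fair criticism is that the unit is ambiguous; a reader who infers that none is stated goes too far. If the Group B statement covers all 17 patients, that side is not selected on pain after the analgesic ended, and 6 or more Group A users would make the paired result for that window significant. The Group A figure would still be conditional on pain.

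Graphics 1 and 2 are not available here and may show the size of the subset. Their captions concern pain reports, not rescue use, so they are unlikely to supply a paired rescue table.

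Several stronger readings are tempting but not supported:
- That the effect is absent or reversed. The documents report no Group B rescue use, so scenarios with Group B users are hypothetical. Mean pain on day 1 was higher in Group A (3.59 vs 2.12), so early codeine use may well have favoured cryotherapy.
- That counting reports makes the result non-significant. Step 4 shows that it could go either way.
- That the different lower limits for moderate pain (3.1 in Section 4.7, 4 in the captions) changed the subset. With whole-number scores they give the same subset, and no effect is shown.

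It may also be said that McNemar ignores surgery order: Section 6 gives 11 patients with control first, leaving 17 - 11 = 6. That is a fair limitation to note beside the table. It does not justify reporting no paired table.

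**Conclusion.** The statements in Sections 6 and 7 that cryotherapy reduced rescue use are not supported as reported. The evidence is one percentage, conditional on post-treatment pain, without counts, pairing or a test, for a measure that is neither a listed outcome nor in the analysis section.

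If the unit is patients and nobody else used codeine, the paired p-value is 0.125, 0.008 or 0.0005, depending on an unreported denominator. If the unit is daily reports, it cannot be determined. These ranges rest on 80% being rounded to a whole percent and on a two-sided 5% level.

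A reader might infer that the conclusion is wrong. The documents do not show that, and its direction may well be right. The problem is confined to the rescue statements: the Abstract does not make the claim, and the pain result (p = 0.039) does not depend on it.

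**What to change.** From the trial records, report any codeine use on days 0-7 for both sides of all 17 patients as a paired 2x2 table with an exact McNemar p-value, labelled post hoc. Base the rescue statements in Sections 6 and 7 on that table.

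- If only days 3-7 were recorded, give the paired table for those days and limit the statement to that window.
- If no patient-level record exists, remove the rescue claim from Sections 6 and 7.
- Keep the 80% only as a description, with numerator, denominator and unit, and say whether the Group B statement covers all 17 patients.
- State beside the table that three of the 20 patients were excluded, in part for using non-prescribed medication, since this bears on any analysis of analgesic use.

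If codeine use was recorded per patient, no new data are needed. The cost is one table and text edits in Sections 5.1, 6 and 7.

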A strong association was also observed between higher pain intensity reports and increased requests for rescue medication in the control group. These results indicate that failure to use cryotherapy may increase reliance on pharmacological interventions to manage postoperative discomfort, which could otherwise be mitigated through a simple and low-cost intervention such as ice pack application for 30 minutes over a 12-hour period. Therefore, the proposed cryotherapy protocol can be considered a safe and effective approach that enhances postoperative predictability, facilitates complication control, and promotes greater patient engagement in self-care.

Trismus represents a multifactorial postoperative response influenced by surgical trauma, including osteotomy, extracellular fluid extravasation, tissue hemorrhage, and muscle fiber incision. Given the simultaneous occurrence of these factors, significant benefits of cryotherapy are not expected before consolidation of the inflammatory response, which explains the absence of intergroup differences during the first 72 postoperative hours. However, when comparing immediate postoperative measurements with those obtained on postoperative day 7, the control

group exhibited significantly greater mouth opening limitation (Table 2), indicating a longer duration of trismus. This finding is supported by the statistically significant correlation between pain intensity and trismus observed exclusively in the control group (Table 3), suggesting that higher pain levels are associated with prolonged mouth opening restriction. These results were further corroborated by the quality-of-life questionnaire, which revealed greater difficulty in mouth opening among control participants.

Edema did not show statistically significant differences between groups (Table 4), consistent with previous reports. It is hypothesized that superficial ice application may be insufficient to significantly reduce edema due to its limited penetration into deeper muscular and facial tissue planes, thereby restricting its vasoconstrictive effects.

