## 7 CONCLUSION

Postoperative cryotherapy was effective in reducing pain intensity and duration, decreasing the need for rescue medication, and shortening the period of mouth opening limitation after mandibular third molar extraction. This intervention also improved patients' perception of recovery and contributed to a more predictable postoperative course. However, cryotherapy did not demonstrate a significant effect on postoperative edema.

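### The 80% versus 0% rescue-medication contrast comes from a subset selected on post-treatment pain, with no count or test, so the claim of reduced rescue need is not supported as stated

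*Combined protocol and SAP*

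**What the plan says.** Section 4.4 gives the analysed set: three of the planned 20 patients dropped out, "resulting in 34 procedures performed in 17 patients". Each patient supplies one control side and one cryotherapy side.

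Section 4.6 allows rescue medication for pain, trismus or edema that persists "despite the use of prescribed analgesics". It does not tie rescue to the period after scheduled paracetamol ends. Section 4.7 does not list rescue use as an outcome, and section 4.8 plans no analysis of it.

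The rescue result is one sentence in section 5.1. It opens "When moderate-to-severe pain reports were isolated and compared with the need for rescue medication after suspension of the standard analgesic regimen" and then states that "80% of participants in Group A required rescue medication, whereas no participant in Group B required additional analgesia". The captions of Graphics 1 and 2 in the same section use pain reports after day 2 as their base.

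The Discussion says that cryotherapy reduced the need for rescue medication and that its absence raised the probability of needing it. It adds: "A strong association was also observed between higher pain intensity reports and increased requests for rescue medication in the control group". The Conclusion lists "decreasing the need for rescue medication" among the effects of cryotherapy.

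**The concern.** The result is worded as a share of participants, but the first half of the sentence describes a selection made on pain after surgery. Section 5.1 reports that treatment changed pain, so the patients or reports entering this subset on the two sides are not comparable by design. Conditioning on them gives up the within-patient pairing, which is the main strength of a split-mouth trial.

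Without a numerator, a denominator and a unit, a reader cannot rebuild the comparison on all 17 pairs. The same printed 80% is compatible with a non-significant result and with a strong one. One of the effects named in the Conclusion rests on it, and the Discussion extends the message to patients with systemic disease and to those susceptible to medication dependence.

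**Working it through.** **Inputs.** 17 patients, each with an A and a B side (section 4.4; the F(1,16) in section 5.1 agrees). Pain was recorded on days 0 to 7, which is 8 time points (the F(7,112) agrees: 7 × 16 = 112). Pain-category shares and the rescue figures are from section 5.1. Alpha is 0.05 (section 4.8); sidedness is not stated, and two-sided is assumed.

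**Step 1: try to reproduce the 80% on participants.** 0.80 × 17 = 13.6. The nearest counts are 13/17 = 76.5% and 14/17 = 82.4%, so the figure does not reproduce. Among denominators up to 17, only 4/5, 8/10 and 12/15 give 80%.

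**Step 2: what unit does the section use?** The pain-category shares reproduce on 17 × 8 = 136 patient-day reports:

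| Category | Group A | Group B |
|---|---|---|
| None | 40/136 = 29.4% | 60/136 = 44.1% |
| Mild | 68/136 = 50.0% | 65/136 = 47.8% |
| Moderate | 23/136 = 16.9% | 10/136 = 7.4% |
| Severe | 5/136 = 3.7% | 1/136 = 0.7% |
| Sum | 136 | 136 |

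As a set they do not reproduce on 17. Mild pain is nevertheless described as a share of participants, so the section already words a report-level share as a participant share. The 80% may do the same. Group A has at most 23 + 5 = 28 moderate-to-severe reports over all days, and with reports as the unit 16/20 and 20/25 would also fit.

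**Step 3: are the selected sets comparable?** Over all days, moderate-to-severe reports number 28 in A and 10 + 1 = 11 in B. The split after day 2 is not given in the text, but the two subsets probably differ in size. Selection is on pain, for which section 5.1 gives a treatment effect of p = 0.039 and states that "A significant interaction between treatment and time was also observed" (p = 0.013).

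**Step 4: re-base on 17 pairs.** Assumptions, none stated in the documents: the 80% counts people; no Group B patient used rescue; no Group A patient outside the subset did. With k users on the A side only and none on the B side only, the two-sided exact McNemar p is 2 × 0.5^k.

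| 80% means | Group A users of 17 | 95% CI (Clopper-Pearson) | p |
|---|---|---|---|
| 4/5 | 4 = 23.5% | 6.8 to 49.9% | 0.125 |
| 8/10 | 8 = 47.1% | 23.0 to 72.2% | 0.008 |
| 12/15 | 12 = 70.6% | 44.0 to 89.7% | 0.0005 |

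The threshold lies between k = 5 (p = 0.0625) and k = 6 (p = 0.031), so at least 6 versus 0 is needed for p < 0.05. For 0/17 in Group B, the upper 95% limit is 1 − 0.025^(1/17) = 19.5%.

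**The case against.** The strongest reply is that nothing is concealed: the sentence carrying the 80% also states the selection and the window. That is right. A reader might infer a hidden subset, and the text does not support this. The defect is a participant label on a subset figure with no counts.

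Several further points stand.

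- The abstract does not mention rescue use, so the claim is one of several in the Discussion and Conclusion.
- Asking about rescue after scheduled paracetamol ends is a coherent question. A reader might call that window an error, but it is only incomplete as a measure of overall rescue need.
- Graphics 1 and 2 are not shown and might carry counts, although their captions describe pain reports and not rescue users.
- Other sources of a non-17 base are possible. The 31% in section 5.4 is not a share of 17 either (5/17 = 29.4%, 5/16 = 31.25%), so missing responses could contribute. Loose rounding of 14/17 is also conceivable, though the isolating clause and the one-decimal percentages nearby argue against it.
- Person-level p-values do not apply if the unit is reports.
- No section describes how rescue use was recorded. Appendix B does not mention rescue medication, and Appendices C and D have no field for it, so a full re-tabulation may not be possible.

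These points limit the size of the finding. They do not supply the missing denominator or undo the selection on pain.

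**Conclusion.** The concern holds in this form: the 80% is not a share of the 17 Group A participants, it is conditioned on a post-treatment outcome, and it comes with no count, test or interval. The statements in the Discussion and Conclusion that cryotherapy reduced rescue need are therefore not supported as written. The description of the association as strong has no reported analysis behind it.

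Under the three assumptions in the working, the paired result runs from p = 0.125 to p = 0.0005. Two of the three person-level readings would be significant. Rescue use outside the subset, on either side, would change these figures.

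A reader might go further and infer that cryotherapy had no effect on rescue use. The documents do not support that: the direction favours cryotherapy, and what is missing is quantification. Nor does the point weaken the pain result, which rests on a separate ANOVA. Finally, using all 17 pairs removes the selection on pain but does not restore the full randomised set. Three patients were excluded for noncompliance and use of non-prescribed medication, which also occurred after treatment.

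**What to change.** 1. In section 5.1, state the numerator, denominator and unit behind both the 80% and the 0, and say whether the zero refers to all 17 patients or to the subset. Label the present contrast as a descriptive, post hoc subset figure.
2. Where rescue use was recorded per patient, report the number of users out of all 17 on each side over the whole recorded period: days 0 to 7 if available, with days 3 to 7 shown separately. Compare the sides with an exact McNemar test. Label it post hoc in both 4.8 and 5.1, because the results are already known.
3. Remove the description of the association as strong unless a patient-level analysis is given.
4. Make the rescue statements in sections 6 and 7 depend on the all-17-pairs result, or drop them if the data do not exist.

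If the records exist, the cost is one tabulation and one exact test. The 80% will probably fall, and the rescue conclusion may have to be softened.
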